**Document History Table**

	Version/Update Date
Amendment # 1	May 12, 2020
Original & Activation	January 24, 2018

### Summary of Changes

Protocol Amendment # 1

Protocol Version Date: May 12, 2020

#	Section	Comments
1	Footer	The protocol version and amendment number has been updated.
2	8.1	Due to COVID-19, Amendment # 1 is to allow study procedures that may need to be conducted remotely, if necessary.
3	9.1	The following sentence has been added as the last sentence of the paragraph, “Due to COVID-19, these study procedures may be conducted remotely, if necessary.”
4	9.5.2	The following sentence has been added as the last sentence of the paragraph, “Some of these study procedures may be conducted remotely, if necessary.”
5		

## **1.0 OBJECTIVES**

- 1.1** Primary: Confirm the technical feasibility of focal prostate stereotactic body radiotherapy (SBRT) with real time guidance by intra-urethral radiotransponder beacons.
- 1.2** Secondary: Clinically assess early efficacy, late toxicity, and quality of life for men receiving focal prostate SBRT for low and low-intermediate risk prostate cancer.

## **2.0 BACKGROUND AND RATIONALE**

### **2.1 Prostate cancer overview**

Prostate cancer is the most common non-cutaneous malignancy among men, with over 180,000 annual incident cases leading to an estimated 28,600 deaths in 2016. Men with prostate cancer are grouped into low, intermediate, or high risk cohorts according to risk stratification schemes based upon well-established risk factors including PSA level, Gleason score (histologic grade), and clinical stage. Definitive treatment options for patients with clinically localized prostate cancer include radical prostatectomy, external beam radiotherapy (RT), and brachytherapy or a combination of external beam RT and brachytherapy, with or without androgen deprivation (ADT).

For men without high risk features, active surveillance is an alternative strategy to definitive treatment. The decision to initiate therapy is based on the patient's life expectancy, individual risk factors, and goals. Currently, the National Comprehensive Cancer Network (NCCN) recommends active surveillance for men with newly diagnosed low risk prostate cancer; however, more than half of men will develop indications for definitive treatment within 10 years.

### **2.2 Rationale for focal therapy for prostate cancer**

Traditional prostate cancer therapies such as surgical resection (prostatectomy) and traditional radiation therapy involve treatment of the entire prostate gland. Currently, men who are diagnosed with low or low-intermediate risk prostate cancer must therefore choose between active surveillance or whole prostate treatments, which can result in significant morbidity. Since many of these men would likely have indolent prostate cancer that would not become life threatening, the morbidity of traditional whole prostate treatment options may not justify their use.

Focal therapy for prostate cancer may offer an ability to improve the risk-benefit ratio of therapy for early prostate cancer by reducing the morbidity of treatment while maintaining oncologic efficacy. Since about half of men who initially elect for active surveillance will undergo definitive treatment within 10 years, earlier intervention with focal therapy may

actually have the potential to lower the overall symptom burden from prostate cancer by reducing the need for more toxic treatments.

### **2.3 Current state of focal therapy for prostate cancer**

Focal therapy options have yet to be fully endorsed by national professional groups such as the NCCN or American Urological Association; however, national patterns of care studies indicate that focal therapy is becoming increasingly utilized. The three most common forms of focal therapy utilized currently are high-intensity focal ultrasound (HIFU), photodynamic therapy, and cryoablation, with each modality having relative strengths and weaknesses. While significant heterogeneity among previous studies, biochemical control among well-selected patients who have also undergone multiparametric MRI appear to fall within the range of 60-85% at 5-years. By comparison, the 5-year biochemical control of men with low-risk prostate cancer who undergo definitive radiation therapy or radical prostatectomy exceeds 90% among nearly all modern series.

### **2.4 SBRT for prostate cancer**

The rationale for prostate SBRT stems from a combination of the theorized sensitivity of prostate cancer to larger fractions of radiation (i.e. low  $\alpha/\beta$ ) in combination with the ability of modern radiation planning, targeting, and delivery techniques to accurately administer higher doses of radiation with small uncertainty margins. A growing body of literature supports that prostate SBRT, typically with a dose of 36.25 Gy to the entire prostate over 5 fractions, is associated with toxicity rates similar to fractionated regimens. Early efficacy results also support that whole prostate SBRT is associated with high rates of biochemical control for men with NCCN defined low or low-intermediate risk prostate cancer. Recently, prostate SBRT was endorsed by the American Society for Therapeutic Radiation Oncology as an option for first-line therapy for men with low-risk prostate cancer.

At the University of Alabama at Birmingham prostate SBRT, has generally been performed as part of a recently completed prospective clinical trial (NCT01856855). In this study, the entire prostate gland was treated to a dose of 36.25 Gy in 5 fractions and MRI-defined focal nodules received a simultaneous integrated boost to 40 Gy in 5 fractions. This study met its primary safety endpoint of fewer than 15% of patients experiencing acute urinary retention requiring temporary placement of a Foley catheter (7.7% observed rate). Biochemical follow-up data are maturing.

### **2.5 Rationale of SBRT for focal treatment**

Despite the fact that whole gland prostate SBRT is associated low rates of severe grade 3 genitourinary (GU) and gastrointestinal (GI), with adverse effects rates on the order of 1%, lower grade late toxicities are

significantly more common. The most common grade 2 late complications include hematochezia (5-15%), diarrhea (5-10%), hematuria (10-15%), and urethral stricture causing urinary retention (5-10%). Erectile dysfunction will also manifest in more than half of men who are sexually active prior to radiation therapy. By reducing the irradiated volume with focal SBRT, radiation dose to the tissues responsible for the toxicities associated with whole-prostate radiation may be reduced.

One key advantage of SBRT over current focal therapy modalities is the ability to account for microscopic disease extension beyond the imaging abnormality. Whole mount pathology correlate studies have consistently shown that microscopic prostate cancer may extend up to 1 cm beyond the lesion seen on MRI. This discrepancy between imaging and pathologic tumor extension poses a challenge for conventional focal therapies such as HIFU and cryotherapy due to the relatively small area of tumocidal effect around the interstitial probe. In order to account for this limitation, the probe is generally placed in multiple positions in and around the lesion; however, this technique is operator dependent and time consuming. In contrast, SBRT planning techniques allow for the target volume to be enlarged to account for microscopic disease extension (i.e. a clinical target volume expansion) beyond the MRI-defined nodule. Since expansions will generally consist of a geometric margin around the nodule they are less susceptible to inter-operator differences.

Another potential advantage of the SBRT technique proposed in this trial over previously described focal therapy techniques is the ability to administer treatment without violating the perineum. Cryotherapy, HIFU, and photodynamic therapy all require placement of a transperineal interstitial probe. Though the rate of severe complication from probe placement is extremely low, this invasive procedure is uncomfortable and necessitates the use of sedation or anesthesia.

## **2.6 Role of radiotransponder beacons in prostate cancer**

The primary technical challenge anticipated for the use of SBRT as a focal therapy modality is managing inter- and intra-treatment target position verification and monitoring without interfering with our ability to accurately delineate the focal nodule. Accurate target verification and monitoring is a vital component of SBRT since it allows for reduction in the size of the planning target volume (PTV) expansion.

The most common technique to confirm the positioning of the prostate before and during treatment is transperineal implantation of radiopaque fiducial markers or Calypso radiotransponder beacons within the prostate gland. The position of radiopaque beacons can be confirmed prior to treatment with orthogonal kV radiographs and cone beam CT. Orthogonal radiographs can also be performed during radiation delivery

[figure not shown]
to provide intra-treatment of target positioning. The position of radiotransponder beacons are continuously assessed via an electromagnetic tracing station which is placed slightly above the patient. The advantage of radiotransponder beacons over radiopaque fiducial markers is that the Calypso system allows for constant verification of the 3-dimensional position of the beacons whereas each kV radiograph provides only a 2-dimensional projection.

## **2.7 Rationale for intra-urethral radiotransponder beacons**

Unfortunately, both radiopaque fiducial markers and radiotransponder beacons have the potential to significantly interfere with accurate targeting of MRI-defined focal nodules. For instance, markers placed into the prostate prior to MRI acquisition will result in significant artifact that may obscure visualization of the nodule. On the other hand, if the markers are placed into the prostate after the MRI is acquired, this could result in subtle changes in prostate anatomy that have the potential to result in a marginal miss. Historically this issue was considered of little clinical significance since the target volume has consisted of the entire prostate gland which, unlike focal nodules, is visible on the CT scan obtained for SBRT planning. However, we believe that the ability to accurately delineate the focal nodules is paramount for focal therapy thus another method is needed to maintain MRI image quality.

Temporary placement of radiotransponder beacons within the urethra (via a Foley catheter, with technique to be described subsequently) will allow for removal of the beacons during imaging to prevent artifact. Since the radiotransponder beacons will be removed following delivery of SBRT, future MRIs obtained for follow-up will not be subject to severe artifact. An additional advantage of intraurethral placement of the radiotransponder beacons is that this technique will obviate the need for needle placement through the perineum

### 3.0 SCHEMA

- 3.1** Patients who meet the enrollment criteria will be enrolled following the decision to proceed with RT for pathologically proven prostate adenocarcinoma. N=10 patients will be enrolled in the study.
- 3.2** Baseline urinary symptoms, rectal symptoms, sexual function, and global quality of life will be assessed using validated patient-reported questionnaires.
- 3.3** A 3-Tesla pelvic MRI containing an axial T2 sequence will be performed without a rectal coil. The use of IV contrast is at the discretion of the treating physician. If an MRI obtained within 3 months prior to enrollment

is deemed clinically acceptable for treatment purposes by the treating physician then reacquisition is not necessary.

- 3.4** CT simulation will be performed with a Foley catheter in place. Radiopaque dummy seeds will be used to mark the anticipated location of the radiotransponder beacons within the catheter.
- 3.5** Utilizing available clinical data (biopsy, physical exam, MRI/MRS, and CT-simulation) physicians, medical dosimetrists, and physicists will create and approve a treatment plan if all dosimetric and quality assurance measurements are met (see sections 6.3 – 6.5). Prescribed dose will be 8.0 Gy per fraction for a total of 5 fractions.
- 3.6** SBRT will be delivered in 9 to 17 calendar days, with every other day fashion in an outpatient clinic setting with an every-other day fashion treatment schedule (see section 6.8). Intraurethral radiotransponder guidance will be performed for all treatments (see section 6.6.4).
- 3.7** Following completion of treatment, patients will be evaluated with clinical exams, laboratory PSA testing, and quality-of-life questionnaires at regular intervals (1, 3, 6, 9, 12, 18, and 24 months post-radiation)
- 3.8** Post-treatment multiparametric MRI and biopsy 1 year from completion of SBRT.

## **4.0 PATIENT SELECTION CRITERIA**

### **4.1 Inclusion criteria**

- 4.1.1** All patients must have histologically confirmed adenocarcinoma of the prostate, with biopsies obtained within 12 months of registration
  - 4.1.1.1** Gleason score 3+3 or 3+4
  - 4.1.1.2** PSA <10 ng/mL within 3 months of enrollment
  - 4.1.1.3** Clinical stage T1a-T2a by digital rectal exam
  - 4.1.1.4** Up to 2 intraprostatic nodules visible on MRI, with combined volume <50% of the total prostate volume
- 4.1.2** Karnofsky Performance Status (KPS) >70%.
- 4.1.3** Life expectancy >10 years
- 4.1.4** Age  $\geq$  19 years

4.1.5 Subjects given written informed consent

**4.2 Exclusion criteria**

- 4.2.1 >2 MRI defined nodules representing prostate cancer
- 4.2.2 Total volume of MRI nodules exceeding 50% of total prostate volume
- 4.2.3 Positive biopsy core in sextant region without MRI defined nodule (i.e. biopsy proven MRI occult prostate cancer)
- 4.2.4 American Urological Association (AUA) urinary score  $\geq 18$ .
- 4.2.5 History of inflammatory bowel disease.
- 4.2.6 Prior pelvic surgery
- 4.2.7 Prior treatment for prostate cancer
- 4.2.8 Patients using immunosuppressive medications or other medications that may increase radiation toxicity such as methotrexate, sirolimus, tacrolimus, or colchicine that are unable to discontinue these medications during SBRT course. Use of corticosteroids is not considered an exclusion criteria.
- 4.2.9 Platelet count  $< 70,000/\mu\text{L}$
- 4.2.10 Patients unable to discontinue anti-platelet or anti-coagulant medicine such as clopidogrel, dabigatran, warfarin, or low molecular weight heparin. Use of aspirin is not an exclusion criteria.
- 4.2.11 Contraindication to MRI such as implanted devices.
- 4.2.12 Metallic pelvic implants resulting in imaging artifact within the prostate on MRI or CT.

**5.0 DRUG INFORMATION**

No experimental drugs are utilized in this study.

**6.0 TREATMENT PLAN**

**6.1 MRI acquisition**

Patients enrolled on this study will undergo acquisition of a 3-T MRI containing an axially acquired T2 sequence without a rectal coil. If a pre-biopsy 3T MRI has been obtained within three months of patient enrollment and is deemed clinically acceptable for treatment planning purposes by the treating physician, then reacquisition of post-biopsy MRI is not necessary.

## **6.2 Treatment planning CT-simulation and contour/volume delineation**

- 6.2.1 Patients will undergo a pre-treatment CT-simulation scan in the supine position. Patients will be instructed to have a full bladder and an empty rectum during CT-simulation. A 16-french Foley catheter will be placed with dummy seeds instead of radiotransponder beacons (see Section 6.7).
- 6.2.2 CT-simulation images will be electronically fused with MRI images within the treatment planning software and are to be used for contours and treatment planning
- 6.2.3 The treating physician will define the prostate, gross tumor volume (GTV), and adjacent organs at risk. The GTV will be defined as the T2 hypodense nodule along with any other area suspicious for tumor based on other available clinical data such as other sequences from the multiparametric MRI.
- 6.2.4 The clinical target volume (CTV) will consist of a 0.5 cm expansion around the GTV but shall not extend beyond the capsule of the prostate or into the urethra.
  - 6.2.4.1 A CTV expansion of 0.5 cm was chosen after considering reports of studies correlating MRI imaging findings with whole-mount pathology specimens.
- 6.2.5 The planning target volume (PTV) consists of a volumetric expansion of the CTV by 3mm in all directions.
- 6.2.6 Adjacent organs at risk to be contoured include the bladder, rectum, bilateral femoral heads, bowel, urethra, and penile bulb.
- 6.2.7 Naming conventions for target volumes and organs at risk will follow the AAPM TG-263 recommendations.
- 6.2.8 The dummy seeds placed in the urethral catheter will be contoured and reviewed by a physicist.
  - 6.2.8.1 The dummy seed contours will be projected onto the reference DRRs of an orthogonal pair of setup fields.

6.2.8.2 The DICOM coordinates of the centroid of each dummy seed and the isocenter will be transferred to the Calypso workstation.

6.2.8.3 The Calypso system will be configured for Gating, Usage Mode: Set zero and track.

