### 6.4 Critical Structures

The organ at risk planning guidelines for the study are given below. All reasonable attempts should be maintained to minimize radiation to organs at risk if PTV coverage is not compromised.

Pilot cohort (40 Gy in 5 fractions)*		
Organ	Volume	Dose (Gy)
Rectum	Maximum point dose (1cc)	≤ 38.06 Gy
	Less than 3cc	< 34.4 Gy
	90% of the rectum	≤ 32.625 Gy
	80% of the rectum	≤ 29 Gy
	50% of the rectum	≤ 18.125 Gy
Bladder	Maximum point dose (1cc)	≤ 38.06 Gy
	90% of the bladder	≤ 32.625 Gy
	50% of the bladder	≤ 18.125 Gy
Urethra	Maximum point dose	≤ 38.78 Gy
Femoral heads	Less than 10cc cumulative (both sides)	20 Gy

	Maximum point dose	30 Gy
--	--------------------	-------

\*Constraints used in prior UAB protocol of prostate SBRT that included 40 Gy in 5 fraction focal boost (NCT01856855).

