## **6.7 Treatment delivery**

- 6.6.1 Patients will be instructed to arrive in the clinic at least 1 hour prior to planned treatment delivery and a 16-french Foley catheter will be placed and urine allowed to drain. A Henschke style catheter containing 3 Calypso radiotransponder beacons will be placed into the urinary lumen of the Foley catheter as shown below:

- 6.6.2 Patients will be instructed to have an empty rectum for treatments. Utilization of bowel preparation with oral or suppository medications is left up to the treating physician. Endorectal balloons are not allowed on this study.
- 6.6.3 Image-guidance with kilovoltage orthogonal x-rays and cone beam CT scans are to be utilized prior to administration of each radiotherapy fraction. A physician is to approve appropriate patient positioning based upon set-up imaging, with the patient being aligned to the urinary catheter and prostate-rectum interface.
- 6.6.4 The positions of the transponders of the KV orthogonal x-rays and the CBCT will be compared with the dummy seed reference contours. The catheter position will be adjusted as needed. After

the patient is correctly positioned, the Calypso reference position (zero) will be set.

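### Simulation asks for a full bladder but urine is drained before treatment, so the percent-volume bladder limits in 6.4 may be assessed on a larger bladder than the one treated

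*Combined protocol and SAP*

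**What the plan says.** **Simulation (6.2.1).** "Patients will be instructed to have a full bladder and an empty rectum during CT-simulation". The same item continues: "A 16-french Foley catheter will be placed with dummy seeds instead of radiotransponder beacons (see Section 6.7". It does not say whether that catheter is drained. Under 6.2.2 and 6.2.6 this scan, fused with MRI, is used for contouring, and the bladder is one of the organs contoured.

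**Treatment (6.7, items printed as 6.6.1 to 6.6.4).** On timing: "Patients will be instructed to arrive in the clinic at least 1 hour prior to planned treatment delivery". On the catheter step that follows arrival: "a 16-french Foley catheter will be placed and urine allowed to drain". A catheter carrying the three beacons then goes into the Foley's urinary lumen. The only preparation instruction is rectal: "Patients will be instructed to have an empty rectum for treatments". Section 3.6 applies beacon guidance to all treatments, so the catheter procedure belongs to every one of the five fractions.

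**Imaging (6.7).** On what is acquired: "Image-guidance with kilovoltage orthogonal x-rays and cone beam CT scans are to be utilized prior to administration of each radiotherapy fraction". On how set-up is then judged: "A physician is to approve appropriate patient positioning based upon set-up imaging, with the patient being aligned to the urinary catheter and prostate-rectum interface". Bladder filling is not among the named criteria.

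**Limits (6.4).** The bladder has three: 1 cc at no more than 38.06 Gy, "90% of the bladder" at no more than 32.625 Gy, and half of the bladder at no more than 18.125 Gy.

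**The concern.** The rectal preparation is the same at both steps and the bladder preparation is not. Staff who follow 6.2.1 plan on a full bladder; staff who follow 6.7 treat after drainage. Nothing in the available text restores the filling or asks anyone to look at it.

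This matters because two of the three bladder limits are shares of the organ. If the same tissue is irradiated and the organ is smaller, the share is larger. A plan can then satisfy 6.4 on the simulation scan while its recorded percentages do not describe the bladder that was treated. Toxicity is a secondary endpoint (11.2). With ten patients, the planned bladder figures are useful for reading any urinary events only if they reflect the treated state.

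**Working it through.** **Step 1. The plan's own figures.** The only design figures are the exact binomial intervals in 11.6.1. For 9 of 10, the Clopper-Pearson interval is (0.5550, 0.9975), width 0.4425. For 10 of 10, the lower limit is 0.025^(1/10) = 0.6915. All reproduce. Bladder volume enters none of them, so they are unaffected.

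**Step 2. The two texts together.** The pointer from 6.2.1 to 6.7 can be read in two ways.
- It covers only the catheter. Then simulation is full and treatment follows drainage, and the two differ as written.
- It brings drainage to simulation as well. Then 6.2.1 asks for a full bladder and a drained one in the same item.

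Under neither reading is one bladder state fixed for both steps.

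**Step 3. What a volume difference would do.** The documents give no bladder volumes and no plan dose-volume data. Assumptions: 50-100 mL drained, 150-300 mL full, and the same absolute volume of bladder above each dose in both states.

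Share above dose = cc above dose / bladder volume. The 6.4 limits allow at most 10% above 32.625 Gy (100% - 90%) and at most 50% above 18.125 Gy.

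Largest compliant volume = limit × bladder volume:

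| Bladder volume | 10% limit (above 32.625 Gy) | 50% limit (above 18.125 Gy) |
|---|---|---|
| 50 mL | 5 cc | 25 cc |
| 100 mL | 10 cc | 50 cc |
| 150 mL | 15 cc | 75 cc |
| 200 mL | 20 cc | 100 cc |
| 300 mL | 30 cc | 150 cc |

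Shares for illustrative plans:

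| Plan | 50 mL | 100 mL | 150 mL | 200 mL | 300 mL |
|---|---|---|---|---|---|
| 4 cc above 32.625 Gy | 8.0% | 4.0% | 2.7% | 2.0% | 1.3% |
| 5 cc above 32.625 Gy | 10.0% | 5.0% | 3.3% | 2.5% | 1.7% |
| 8 cc above 32.625 Gy | 16.0% | 8.0% | 5.3% | 4.0% | 2.7% |
| 12 cc above 32.625 Gy | 24.0% | 12.0% | 8.0% | 6.0% | 4.0% |
| 20 cc above 18.125 Gy | 40.0% | 20.0% | 13.3% | 10.0% | 6.7% |
| 25 cc above 18.125 Gy | 50.0% | 25.0% | 16.7% | 12.5% | 8.3% |

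A plan with 5 cc or less above 32.625 Gy and 25 cc or less above 18.125 Gy meets both limits at every assumed volume. At 8 cc the 10% limit fails only at 50 mL. At 12 cc it is met at 150-300 mL and fails at 50 and 100 mL.

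**Step 4. Sensitivity.** If the drained volume were 30 mL, the thresholds would fall to 0.10 × 30 = 3 cc and 0.50 × 30 = 15 cc.

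**Step 5. The absolute limit.** The 1 cc limit does not scale with bladder volume. A plan that meets it has at most about 1 cc above 38.06 Gy. The 8 cc and 12 cc cases therefore need about 8 - 1 = 7 cc and 12 - 1 = 11 cc of bladder between 32.625 and 38.06 Gy.

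**The case against.** The strongest reply is that no effect has been shown, and several parts of it stand.

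- **The volumes are assumed.** Both the bladder volumes and the cc values come from outside the documents, and Step 4 shows that the thresholds move with them.
- **A focal plan may have room to spare.** The CTV stays within the capsule (6.2.4), the PTV margin is 3 mm (6.2.5), and 6.3.3 gives priority to rapid falloff outside the PTV. The 6.4 limits come from a protocol that treated the whole gland to 36.25 Gy with a 40 Gy boost (2.4 and the footnote to 6.4). Nothing shows that 7 to 11 cc of bladder in the intermediate dose band is likely.
- **The limits are planning guidelines.** Section 6.4 ranks them below PTV coverage, and the documents set no limit on delivered bladder dose.
- **The bladder at beam-on is not known to be empty.** Patients arrive at least an hour ahead, the beacon catheter occupies the lumen after drainage, and the time from drainage to treatment is not stated. Some refilling is possible.
- **Imaging is already in place.** Cone beam CT can show the bladder, and a physician approves the set-up.

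These points limit the size of the concern but do not reconcile the text. Possible refilling makes the treated volume uncontrolled; it does not make it match simulation. The written alignment criteria deal with target position and neither set bladder volume nor check bladder dose.

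**Conclusion.** The point holds as an operational and dosimetric inconsistency that should be corrected. The plan does not fix one bladder state for simulation and treatment, so two of the three bladder limits may be assessed on a larger bladder than the one treated. On the assumptions in Step 3, this can change compliance only above 5 cc at 32.625 Gy or 25 cc at 18.125 Gy. Smaller focal plans may be unaffected.

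A reader might infer that bladder limits will be breached at delivery. The documents do not support that: they contain neither the volumes nor the dose-volume data needed, and they set no delivered-dose limit. A reader might also infer that the feasibility result is compromised. It is not: the 9-of-10 rule counts completion of treatment, and the planned analysis is descriptive (11.5.1).

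**What to change.** **In 6.2.1,** replace the full-bladder instruction. Simulation should follow the same Foley drainage, catheter loading (with dummy seeds) and approximate waiting time as treatment in 6.7. State that the 6.4 bladder limits are assessed on that scan. Because 6.7 gives no interval from drainage to treatment, write an approximate one there.

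**In 6.7,** have the physician who approves the cone beam CT also compare bladder filling with the simulation contour and record the result. This should be an observation, not a go/no-go rule; a stopping rule could delay or halt fractions and so bear on the completion endpoint.

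Matching in the other direction, by restoring a full bladder at treatment, is not proposed because the beacon catheter sits in the urinary lumen.

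**Cost.** A few sentences and slightly more set-up time, with no extra imaging. The planned percent-volume bladder figures become less favourable. Planning feasibility under 9.2.2 refers to 6.4, so a plan above the Step 3 thresholds could find that component harder to meet. N=10, the 9-of-10 rule and the stated intervals do not change.
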